### **5.2.3.2 Concomitant Therapy**

Doses of immunosuppressants (including but not limited to) azathioprine, 6-MP, and methotrexate and aminosalicylates taken at Baseline will be continued. Doses must remain stable throughout the duration of the study. Doses may be decreased or terminated in the event of treatment-related toxicities (e.g., leukopenia or elevated liver enzymes) considered moderate to severe in the opinion of the investigator.

Doses of Crohn's disease related antibiotics taken at Baseline will be continued. Change in dose of Crohn's disease related antibiotics during the study will not be allowed except for treatment related toxicities or concerns about development of antibiotic resistance. Newly prescribed CD related antibiotics is not allowed during the study.

Doses of corticosteroids taken at Baseline, as outlined in inclusion criterion 4 in Section 5.2.1, will be continued. Subjects are not allowed to change the corticosteroid

dose during the first 4 weeks of the study except in the event of treatment-related toxicities considered moderate to severe in the opinion of the Investigator. At Week 4, all subjects who are taking corticosteroid therapy at Baseline will have their corticosteroid therapy tapered according to a tapering schedule specified below and in Section 5.3.1.1.

If the Investigator feels that the steroid taper is not advisable for a particular subject at Week 4, the SDP should be consulted for evaluation and approval.

A proposed regimen to taper prednisone dose starts with a weekly decrease by 5 mg/day prednisone (or equivalent) for doses > 10 mg/day of prednisone (or equivalent) until a 10 mg/day (or equivalent) dose is reached, then a weekly decrease by 2.5 mg/day (or equivalent) until discontinuation. A proposed regimen to taper budesonide dose starts with a weekly decrease by 3 mg/day budesonide until discontinuation.

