Subjects taking corticosteroids at Baseline who have a loss of satisfactory clinical response per the Investigator's judgment after the steroid taper has been initiated may have their corticosteroid dose increased per the Investigator's discretion during the study. Subjects in whom the maximum equivalent steroid dose exceeds the dose used at Baseline will be censored for efficacy assessments (i.e., they will be considered non-responders for categorical endpoints and will have the last non-missing values carried forward for non-categorical assessments) from that point forward. These subjects will continue to be evaluated in the safety population. In addition, subjects in whom the CD-related corticosteroids that were not being taken at Baseline and are initiated during the study will be censored for efficacy assessments (i.e., they will be considered non-responders for categorical endpoints and will have the last non-missing values carried forward for non-categorical assessments) from that point forward. These subjects will continue to be evaluated in the safety population.

Subjects may not be on both budesonide and prednisone (or equivalent) simultaneously.

Subjects who enter the study on probiotics may continue this therapy provided doses remain stable from Baseline throughout the duration of the study.

Subjects in whom the following CD-related medications (oral or rectal aminosalicylates, thiopurines and MTX) that were not being taken at Baseline and are initiated during the study or who have dosages of these medications increased to greater than the dose taken at Baseline is prohibited during the study, except in the event of moderate-to-severe treatment related toxicities and after discussion with the AbbVie TA MD.

Changes in all concomitant medications will be assessed at each study visit from Baseline (Week 0) through Week 56/PD Visits. Any changes will be documented in the source documents and captured on the appropriate eCRF page.

The AbbVie Study Designated Physician identified in Section 6.1.5 should be contacted if there are any questions regarding concomitant or prior therapy(ies).

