5.0 Analysis Populations

5.1 Definition for Analysis Populations

The following populations will be used for analyses in the study:

Modified Intent-to-Treat (mITT) set includes all ITT subjects who achieve clinical response (CR-70) at Week 12. The mITT set is the primary population for the efficacy analysis for the Maintenance Study.

The safety set consists of all subjects who received at least one injection of study drug during maintenance study. The safety set will be analyzed as treated, according to treatment the subject actually received. The safety set will be used only for safety analysis.

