Subjects in whom systemic corticosteroids were used at Induction Baseline and initiated rectal corticosteroids during the study will be censored for efficacy assessment, regardless of rectal corticosteroid dose.

The equivalent steroid dose will be determined based on the table below:

Corticosteroid	Equivalent Dose (mg)
Cortisone	25
Hydrocortisone	20
Prednisone	5
Prednisolone	5
Triamcinolone	4.0
Methylprednisolone	4.0
Betamethasone	0.75
Dexamethasone	0.75
Budesonide	1
Beclomethasone	5
Beclometasone	5

Definition of Missing Data Imputation

The following imputation methods will be used to impute missing values in the efficacy analyses. In addition, an observed case analysis will be performed.

Non-Responder Imputation (NRI)

The NRI approach is used for binary efficacy variables. These variables can take values of 'Achieved' or 'Not Achieved' or may be missing for any reason including discontinuation from study. According to the NRI imputation approach, all missing values will be considered as 'Not Achieved.'

Last Observation Carried Forward (LOCF)

For all variables (categorical variables and continuous variables), the following rules will be used for the LOCF approach:

1. Maintenance Baseline and Pre-Maintenance Baseline values will not be used to impute the missing Post-Maintenance Baseline values.

2. Missing values after Study Day 1 will be imputed using the latest non-missing values after Day 1 and prior to the missing value. If there are no non-missing values after Maintenance Baseline, then the LOCF value will be missing.

Mixed-Effect Model Repeated Measure (MMRM)

The MMRM model will be used for continuous efficacy variables with longitudinal data as a sensitivity analysis. The MMRM model includes the Induction baseline values as covariate; randomization strata, region (US versus non-US), treatment, time point and treatment-by-time point interaction as fixed effects; and subjects within treatment as random effect. An unstructured (co)variance structure will be used to model the within-subject error. The comparison at a time point will be the contrast between treatments at that time point.

Observed Case (OC)

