Observed case analysis will be performed such that missing values will not be imputed. Subjects in whom the following CD-related systemic or rectal corticosteroids that were not being taken at Induction Baseline and are initiated during the study or who have dosages of these medications increased to greater than the dose taken at Induction Baseline will be censored for efficacy assessments (i.e., will be considered non-responders for categorical endpoints and the observed non-categorical assessments will be replaced by last non-missing values prior to censoring) from that point through the end of the study.

Subjects in whom systemic corticosteroids were used at Induction Baseline and initiated rectal corticosteroids during the study will be censored for efficacy assessment, regardless of rectal corticosteroid dose.

Imputation of Missing Dates

For Baseline, efficacy, and safety parameters, if the day and/or month are missing, the following conventions will be used to impute the missing dates:

- 01 for missing start day
- End of month for missing end day
- January 1st for missing start month
- December 31st for missing end month

Rule for CDAI Calculation

Up to 14 days of diary entries will be evaluated from the ePRO tool for the CDAI calculation for each visit. The diary entries on the days the subjects receive endoscopy preparation medications, the day of endoscopy procedure, and 2 days after endoscopy procedure will be excluded. For each CDAI subscore, the available scores from the most recent diary days (at least 4 days, up to 7 days) prior to actual day of the study visit will be summed, and then multiplied by the corresponding multiplier to get subtotal score. If available diary entries are fewer than 7 days, the subtotal score will be calculated as (summed total available score/number of days) \times 7 \times corresponding multiplier. The three subtotal scores that are based on ePRO (number of liquid/very soft stools, abdominal pain rating, and general well-being) will then be rounded to one decimal. The final CDAI is rounded to a whole number.

If a subject has less than 4 days of diary data, the total CDAI score will not be calculated and will be considered missing.

Sensitivity analyses will be performed to make use of all available data based on the above rule if more than 5% of subjects have less than 4 days of diary data.

Definition of Clinical Remission

CDAI < 150.

Definition of Clinical Response

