Subjects in whom the CD-related corticosteroids (systemic or rectal corticosteroids) that were not being taken at Baseline and are initiated during the study or who have equivalent dose of these medications increased to greater than the dose taken at Baseline will be censored for efficacy assessments (i.e., will be considered non-responders for categorical endpoints and will have last non-missing values carried forward for non-categorical assessments) from that point through the end of the study. These subjects will continue to be evaluated in the safety population.

The equivalent steroid dose will be determined based on the table below:

Corticosteroid	Equivalent Dose (mg)
Cortisone	25
Hydrocortisone	20
Prednisone	5
Prednisolone	5
Triamcinolone	4.0
Methylprednisolone	4.0
Betamethasone	0.75
Dexamethasone	0.75
Budesonide	1
Beclomethasone	5
Beclometasone	5

Definition of Missing Data Imputation

The following imputation methods will be used to impute missing values in the efficacy analyses. In addition, an observed case analysis will be performed.

Non-Responder Imputation (NRI)

The NRI approach is used for binary efficacy variables. These variables can take values of 'Achieved' or 'Not Achieved' or may be missing for any reason including discontinuation from study. According to the NRI imputation approach, all missing values will be considered as 'Not Achieved.'

Last Observation Carried Forward (LOCF)

For all variables (categorical variables and continuous variables), the following rules will be used for the LOCF approach:

1. Baseline and Pre-Baseline values will not be used to impute the missing Post-Baseline values.

2. Missing values after Study Day 1 will be imputed using the latest non-missing values after Day 1 and prior to the missing value. If there are no non-missing values after Baseline, then the LOCF value will be missing.

Mixed-Effect Model Repeated Measure (MMRM)

The MMRM model will be used for continuous efficacy variables with longitudinal data as a sensitivity analysis. The MMRM model includes the baseline values as covariate; randomization strata, region (US versus non-US), treatment, time point and treatment-by-time point interaction as fixed effects; and subjects within treatment as random effect. An unstructured (co)variance structure will be used to model the within-subject error. The comparison at a time point will be the contrast between treatments at that time point.

Observed Case (OC)

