Observed case analysis will be performed such that missing values will not be imputed. Subjects in whom the following CD-related systemic or rectal corticosteroids that were not being taken at Baseline and are initiated during the study or who have dosages of these medications increased to greater than the dose taken at Baseline will be censored for efficacy assessments (i.e., will be considered non-responders for categorical endpoints and the observed non-categorical assessments will be replaced by last non-missing values prior to censoring) from that point through the end of the study.

Imputation of Missing Dates

For Baseline, efficacy, and safety parameters, if the day and/or month are missing, the following conventions will be used to impute the missing dates:

- 01 for missing start day
- End of month for missing end day
- January 1st for missing start month
- December 31st for missing end month

Rule for CDAI Calculation

Up to 14 days of diary entries will be evaluated from the ePRO tool for the CDAI calculation for each visit. The diary entries on the days the subjects receive endoscopy preparation medications, the day of endoscopy procedure, and 2 days after endoscopy procedure will be excluded. For each CDAI subscore, the available scores from the most recent diary days (at least 4 days, up to 7 days) prior to actual day of the study visit will be summed, and then multiplied by the corresponding multiplier to get subtotal score. If available diary entries are fewer than 7 days, the subtotal score will be calculated as (summed total available score/number of days) \times 7 \times corresponding multiplier. The three subtotal scores that are based on ePRO (number of liquid/very soft stools, abdominal pain rating, and general well-being) will then be rounded to one decimal. The final CDAI is rounded to a whole number.

If a subject has less than 4 days of diary data, the total CDAI score will not be calculated and will be considered missing.

Sensitivity analyses will be performed to make use of all available data based on the above rule if more than 5% of subjects have less than 4 days of diary data.

Definition of Clinical Remission

CDAI < 150.

Definition of Clinical Response

Decrease in CDAI \geq 70 points from Baseline.

Definition of Enhanced Clinical Response

Decrease in CDAI \geq 100 points from Baseline.

Definition of Endoscopic Remission

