10.2 Primary Efficacy Analyses

This section provides the details of the primary efficacy analysis for the Induction Study.

Co-Primary Efficacy Variables:

- Proportion of subjects who achieve clinical remission at Week 4 (CDAI < 150).
- Proportion of subjects with decrease in SES-CD > 50% from Baseline (or for a Baseline SES-CD of 4, at least a 2 point reduction from Baseline) at Week 12.

Analysis Data Set for the Primary Efficacy Analysis:

The primary efficacy analysis will use the ITT analysis data set.

Imputation Method Used for the Primary Efficacy Analysis:

Missing CDAI at Week 4 or SES-CD at Week 12 will be imputed using the non-responder imputation (NRI) approach.

Statistical Method of the Primary Efficacy Analysis:

The comparisons between treatment groups on the two co-primary efficacy variables will be performed using the Cochran-Mantel-Haenszel (CMH) adjusted for hs-CRP at Baseline (< 10 and ≥ 10 mg/L), prior infliximab use (or prior anti-TNF use for subjects randomized under original protocol), and Crohn's disease severity (CDAI ≤ 300 , > 300) at Baseline. A CMH based two-sided 95% confidence interval for the difference between treatment groups will be calculated. Breslow-Day test for homogeneity of odds ratios will be performed as well. An exact CMH test will be used to handle zero cells.

For Week 4 clinical remission (CDAI < 150), LOCF, OC and multiple imputation methods will be used as sensitivity analyses. For Week 12 endoscopic response, OC will be used as sensitivity analysis.

In addition, as sensitivity analyses, the logistic regression including treatment, the randomization stratification factors and additional clinically important factors such as corticosteroid use at Baseline, IMM use at Baseline, Baseline fecal calprotectin, Baseline SES-CD, and Region (US versus ex-US) will also be performed for the co-primary endpoints.

The co-primary endpoints will be tested prior to the ranked secondary endpoints.

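### Do the SAPs leave it open whether a change from one corticosteroid to another after Baseline makes a subject a non-responder?

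*SAP*

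**What the plan says.** Section 6.0 of the Induction SAP, under the heading on CD-related concomitant corticosteroid therapy, covers systemic and rectal corticosteroids that "were not being taken at Baseline and are initiated during the study or who have equivalent dose of these medications increased" above Baseline. Such subjects become non-responders on categorical endpoints from that point. A table follows in which budesonide 1 mg stands against prednisone 5 mg. The Maintenance SAP has the same rule and table, tied to Induction Baseline.

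The observed-case paragraphs repeat the rule in looser words. In the Induction SAP, subjects "who have dosages of these medications increased to greater than the dose taken at Baseline will be censored for efficacy assessments"; in the Maintenance SAP, subjects "who have dosages of these medications increased to greater than the dose taken at Induction Baseline will be censored for efficacy assessments". Both keep the initiation limb. Neither mentions equivalent dose or the table.

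The Maintenance SAP adds that subjects on systemic steroids at Induction Baseline who "initiated rectal corticosteroids during the study will be censored for efficacy assessment, regardless of rectal corticosteroid dose". The Induction SAP has no such sentence.

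Protocol 5.2.3.2 states that "Subjects may not be on both budesonide and prednisone (or equivalent) simultaneously". It also bars any change in corticosteroid "dose during the first 4 weeks of the study except in the event of treatment-related toxicities considered moderate to severe".

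**The concern.** A subject who moves from budesonide to prednisone, or back, starts a drug not taken at Baseline and also has a new equivalent dose. Under the initiation limb every such subject is censored. Under the dose limb the table decides. Because the two drugs may not be taken together, adding one means replacing the other.

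The choice would set responder status for switchers on Week 12 endoscopic response, on the 10 of 15 ranked secondary endpoints with a Week 12 component (1 to 5, 9, 10, 12, 14 and 15), and on the Week 56 endpoints. It could also bear on the maintenance population, since the "Modified Intent-to-Treat (mITT) set includes all ITT subjects who achieve clinical response (CR-70) at Week 12" and Section 5.1 of the Maintenance SAP does not say whether the censored value is used.

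The change from equivalent dose to dosages suggests a second problem. In Section 10.2 of the Induction SAP, "For Week 12 endoscopic response, OC will be used as sensitivity analysis", and this is the only missing-data sensitivity analysis for that co-primary endpoint. If it censored different subjects from the main analysis, a gap between the two results would mix a censoring change with missing data.

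**Working it through.** **The plan's own power.** Inputs from Induction SAP 4.3: 300 and 200 subjects, Fisher's exact test, two-sided 0.05. Exact enumeration gives 99.4% for 50% versus 30% at Week 4 and 99.8% for 66% versus 44% at Week 12. The plan states 99% and about 99%, so both reproduce. The product, 0.9939 × 0.9978 = 0.992, agrees with the stated joint power above 98%.

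**How far the readings differ.** Take budesonide 3, 6 and 9 mg (15, 30 and 45 mg equivalent by the SAP table) and prednisone 5 to 40 mg in 5 mg steps. The maxima are the entry ceilings in Protocol 5.2.2; the grid itself is an assumption. A switch is censored on the dose limb if the new equivalent exceeds the old.

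- Budesonide to prednisone, 3 × 8 = 24 pairs: 5 + 2 + 0 = 7 censored.
- Prednisone to budesonide, 24 pairs: 3 + 3 + 2 + 2 + 2 + 1 + 1 + 1 = 15 censored.
- Dose limb: 7 + 15 = 22 of 48. Initiation limb: 48 of 48. They differ on 48 − 22 = 26.

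**Whether the main and observed-case analyses part company.**

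| Reading | General rule censors | Observed case censors | Pairs treated differently |
|---|---|---|---|
| Any new agent is an initiation | 48 | 48 | 0 |
| Switches judged by equivalent dose, in both texts | 22 | 22 | 0 |
| Equivalent dose in one text, raw milligrams in the other | 22 | 24 | 15 + 13 = 28 |

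Only the third row separates the two analyses. It requires milligrams of budesonide to be compared directly with milligrams of prednisone, in a section that supplies a conversion table. Section 12.2 of the Induction SAP records a single change to the censoring rule and draws no line between the main and observed-case analyses.

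**Rectal steroids.** The Induction rule names rectal corticosteroids. Under the initiation limb, a systemic user who starts one is censored, as in the Maintenance SAP. Under the dose limb, a rectal steroid added to an unchanged systemic dose also raises the total. Only rectal use during or after a systemic taper stays open, and Protocol 5.2.3.3 prohibits therapeutic enemas and suppositories during the study.

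**Size.** One reclassified subject moves an arm's rate by 1/300 = 0.33 points or 1/200 = 0.50 points. The documents give neither the share on steroids at Baseline nor a switch rate. Assume 20% to 50% on steroids and 2% to 10% of those switching: 500 × 0.20 × 0.02 = 2, up to 500 × 0.50 × 0.10 = 25 subjects.

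- All set to non-response, equally in both arms: at 25 subjects (5%), 0.66 × 0.95 = 62.7% versus 0.44 × 0.95 = 41.8%, power 99.5%; at 2 subjects, 99.8%.
- 5% of the higher arm only: 62.7% − 44% = 18.7 points, power 98.2%.
- Ranked secondary 4, restricted to Baseline steroid users: the higher arm has 60 to 150 subjects and the standard arm 40 to 100, so one subject moves a rate by 0.7 to 1.7 or 1.0 to 2.5 points.

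**The case for a change.** The best case for a change is that the text supports both readings. A conversion table is needed mainly to compare different drugs, so if every change of drug is an initiation the table has little to do in this section. The Maintenance sentence on rectal steroids would likewise be redundant. Protocol 5.2.3.2 first treats Baseline users by equivalent dose and then, as an addition, steroids not taken at Baseline, which suggests that users are judged by dose and non-users by initiation. Against this, the words on initiation carry no exception for switches. Two programmers could derive different flags. Ranked testing stops at the first failure, so a few subjects could matter at a borderline step, and a choice made after unblinding could look driven by results.

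Much of this stands: no sentence names the switch, and the reading should be settled before anyone sees results by arm. But it shows a missing detail, not a rule that yields a wrong estimate. The table also has a use elsewhere, because Section 7.3 of each SAP tabulates Baseline steroids in prednisone equivalents. Replacing one steroid with another is not among the changes listed as allowed in Protocol 5.1, so nothing suggests that switches are common. The count of 26 in 48 is not a frequency: it weights all pairs equally and stops at the entry ceilings, whereas the taper section of Protocol 5.3.1.1 allows later increases beyond the Baseline dose.

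The question of which CR-70 value defines the maintenance population is separate. It arises for every censored subject, not only switchers, and concerns analyses that the protocol calls exploratory.

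**Conclusion.** No change to the plan follows. The wording is loose in three places, but each can be read consistently across the general rule, the observed-case analysis and both SAPs. The analyst has to settle one reading and derive one flag for all efficacy analyses, as would be done in any programming specification. An extra sensitivity analysis counting all switches as non-response, and a table of switchers, would be optional and would correct no stated rule.

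The size is unknown and probably small. On the assumed range of 2 to 25 affected subjects, spread equally over the arms, Week 12 power stays at 99.5% to 99.8%; in the one-sided case of 5% of the higher arm it is 98.2%. The Week 4 co-primary endpoint is largely protected by the restriction on early dose changes.

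This conclusion assumes that switches are uncommon, that the reading is fixed before unblinding, and that the same flag serves the main and observed-case analyses. It takes no position on the equivalence ratio or on how steroids should be managed.
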